#### SfE CORE Study Protocol

in scope, falling short of achieving a comprehensive national overview. Should this project succeed in gathering adequate data, this system will be commissioned as the NHS-standard platform for such data collection.

Our target is to engage 50% of specialist weight management service to use this system and capture 80% of essential data points for 60% of patients attending these clinics. Each weight management service typically receives approximately 700 patient referrals annually, with patients spending an average of 18 months in the program. We plan to recruit patients for two years, tracking outcomes for the duration of their clinic attendance. Data entry can be retrospective, allowing us in the first year to gather data on approximately 1,050 existing patients ( $700 \times 1.5$ ) and 700 newly referred patients each in the first and second years, leading to a potential recruitment of 2,450 patients per service.

Assuming an 80% capture rate, we anticipate enrolling 1,960 patients per clinic, resulting in a total of 41,160 patients across 21 participating sites.

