#### Data analysis

The primary outcome of this study is the number of clinics collecting data. Our aim is to get 50% of specialist weight management service using the database. We will report the number of specialist weight management service and what percentage of clinics are using the app at year 2 of the project.

The secondary outcomes of this study are the percentage of patients who we capture data on, and the percentage of data captured on key variables. Our aim to capture data on 60% of patients who attend the services and of those who sign up to the study aim to capture key data on 80% of these patients. The percentage of people we capture the data on will be = (the number of people we have data on/the number of people who attend the clinic) X 100. The percentage of key variable will be worked out for each variable and will be = (number of variable entered/ number of variable possible) x 100.

For the exploratory analysis we will use simple stats (mean, median, SD, interquartile ranges and percentage) to describe the demographic and clinical characteristics of the people entered into the database. Multivariable linear regression will be used to look at the change in weight, BMI, EQ5D and Body Q scores over 12 months and to determine if this is influenced by treatment modality and demographic groups. All analysis will be done in STATA.

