### **10.2 Appendix 2 – Schedule of Procedures**

Timepoint	Event
Baseline	Informed Consent, Clinical Data Collected, Questionnaires (EQ5D and BODYQ) via Patient app, clinical data collected
Every 12 months until exit of clinic or study ends	Clinical Data Collected, Questionnaires (EQ5D and BODYQ) via Patient app
Triggered patient data collection	Upon notification every 3 months, patients will be invited to update treatments and symptoms. If there are new additions then a triggered EQ5D and BODYQ will be asked of the patient via the patient app.

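### About 43% of planned recruits are already in treatment when they consent, and the exploratory 12-month change analysis neither fixes their time zero nor separates them from new referrals

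*Protocol*

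**What the plan says.** Protocol section 6.2.1 starts from two planning figures: "Each weight management service typically receives approximately 700 patient referrals annually, with patients spending an average of 18 months in the program". From these it takes the existing caseload, "Data entry can be retrospective, allowing us in the first year to gather data on approximately 1,050 existing patients", and adds "700 newly referred patients each in the first and second years, leading to a potential recruitment of 2,450 patients per service". Section 6.1 admits any attender of a participating service, with no restriction to new referrals.

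The baseline row of Appendix 2 reads "Informed Consent, Clinical Data Collected, Questionnaires (EQ5D and BODYQ) via Patient app". Section 4, Data collection, has patients fill in the app, questionnaires included, once they have consented. Staff enter clinic measurements and treatments.

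Section 4, Data analysis, states: "Multivariable linear regression will be used to look at the change in weight, BMI, EQ5D and Body Q scores over 12 months". The influences it names are treatment modality and demographic group; time already spent in the service is not mentioned. Section 3.2 lists these analyses as exploratory.

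**The concern.** A new referral's 12-month change covers the first year of care. An existing patient's change, counted from consent, covers a later stretch. If every stay lasted exactly 18 months (an assumption), existing patients would be 9 months in on average, so the stretch would run from about month 9 to month 21, and many would leave before its end. These are different quantities under one label.

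Existing patients are also selected. Anyone who left before the site opened cannot be among them, so they over-represent people who stay.

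If modalities, demographic groups or areas differ in their proportion of existing patients, their mean changes can differ for that reason alone. Section 2 says the study should allow statements on how effective the services are, whether that varies by area, and how interventions perform in practice. Those statements would draw on this analysis.

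**Working it through.** **1. The plan's own projection (inputs from section 6.2.1)**
- Existing: 700 × 1.5 = 1,050 per service.
- New: 700 + 700 = 1,400 per service.
- Total: 1,050 + 1,400 = 2,450; × 0.80 = 1,960; × 21 = 41,160.

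This reproduces the plan exactly: "Assuming an 80% capture rate, we anticipate enrolling 1,960 patients per clinic, resulting in a total of 41,160 patients across 21 participating sites".

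**2. Share of recruits already in treatment**
- 1,050 / 2,450 = 42.9%, which is 840 of 1,960 per clinic and 17,640 of 41,160 overall.
- A common capture rate cancels. At the target given in the same section, "capture 80% of essential data points for 60% of patients attending these clinics", the figures are 13,230 of 30,870, again 42.9%.

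**3. Which baseline applies to existing patients**
- EQ5D and BodyQ: first completed after consent, so necessarily mid-treatment. Retrospective entry cannot supply scores that were never collected.
- Weight and BMI: Appendix 2 lists clinical data in the same row as consent, but section 6.2.1 allows retrospective entry. Either value could serve, and no section chooses. With the clinic-entry value the mixing of treatment phases disappears, but selection of those who stayed remains.

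**4. Who can supply a 12-month change counted from consent**

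This applies to the questionnaires, and to weight and BMI only if consent is their baseline. Data collection ends at month 24 + 6 = 30 (section 7.5, Definition of the end of trial). New patients must therefore enter by month 18: 700 + 350 = 1,050 per service. The documents give only a mean stay, so three sets of assumptions are shown.

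| Assumption | Existing with 12 months left | New with 12 months | Existing share |
|---|---|---|---|
| Every stay 18 months; existing patients' consent spread evenly over year 1 | 1,050 × 1/12 = 87.5 | 1,050 | 87.5 / 1,137.5 = 7.7% |
| Every stay 18 months; all existing patients consent at opening | 1,050 × 6/18 = 350 | 1,050 | 350 / 1,400 = 25% |
| Exponential stays, mean 18 months; all existing patients consent at opening | 1,050 × exp(−12/18) = 539 | 1,050 × exp(−12/18) = 539 | 50% |

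**5. Effect on the pooled mean**

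Let s be the existing share. Let r be existing patients' 12-month change from consent divided by new patients' 12-month change from entry. Then pooled change / new-patient change = (1 − s) + s × r. The documents do not give r, so the values below are illustrative.

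| s | r = 0 | r = 0.5 | r = 1 | r = 1.2 |
|---|---|---|---|---|
| 7.7% | 0.92 | 0.96 | 1.00 | 1.02 |
| 25% | 0.75 | 0.88 | 1.00 | 1.05 |
| 50% | 0.50 | 0.75 | 1.00 | 1.10 |

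The pooled mean is too low if r < 1, unaffected if r = 1 and too high if r > 1.

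**The case against.** The strongest reply has four parts.

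- **This may belong elsewhere.** The full covariate list and time origin of an exploratory model are commonly left to the SAP, which is not at hand. The data dictionary listed in Appendix 1 is not shown either and may already hold a first-attendance date. This stands in part: pooling is what the protocol describes, but a later document could separate the groups. It could do so reliably only if the date is collected, and the data items listed in the protocol do not include it.
- **Retrospective entry may cure it.** For weight and BMI it could, if the clinic-entry value were named as baseline. It cannot for the questionnaires.
- **Earlier treatment is visible.** Section 3.2 asks for start dates of weight-loss drugs, start and finish dates of low-calorie diets, and dates of psychology sessions. This stands. Treatments begun before consent can be identified, so a claim that they will be mislabelled would go too far.
- **Only exploratory analyses are touched.** This stands. Clinic uptake, patient capture and data completeness do not depend on it.

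A reader might also infer that pooling understates what the services achieve, or that clinics with many existing patients will look worse. The documents support neither. They give no weight or questionnaire trajectory, and patients who stay may do better as well as worse. The projection also uses the same mix for every service.

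**Conclusion.** The point holds as a gap in definition that can bias the exploratory change analyses. The 42.9% is exact on the protocol's figures, but it describes recruits. Among those who can supply a 12-month change from consent, the share could be about 8% to 50%, and that range rests wholly on assumptions about stays and consent timing. Mid-treatment baselines are certain for existing patients' EQ5D and BodyQ; for weight and BMI the baseline is undefined. No direction or size of bias can be claimed, because r is unknown. The matter is worth correcting because section 2 attaches effectiveness statements to these data, but it does not threaten the proof-of-concept aim.

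**What to change.** 1. Record the date of first service attendance for every participant, unless the data dictionary already holds it, and settle this before data entry begins.
2. Define time zero as service entry and classify each participant as new or existing from that date.
3. Run the main version of the 12-month change, treatment-modality and outcome-disparity analyses in new referrals.
4. Report existing patients separately. For weight and BMI, use the back-entered clinic-entry value. Compute no questionnaire change from entry for them.
5. Keep existing patients in the cross-sectional description and the capture rates.

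The cost is one date field, some analysis wording and fewer patients in the change analyses. Up to about 1,050 new patients per service have 12 months of calendar follow-up by month 30, before capture rate and early leavers. At 60% capture that is 1,050 × 0.60 = 630 before early leavers.

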### 1 BACKGROUND

Obesity is an escalating issue in the UK, which currently has the highest obesity rate in Europe [1]. Approximately 27% of the adult population is classified as obese, contributing significantly to the primary care workload, with obesity associated with 44% of Type 2 diabetes cases, 23% of ischaemic heart disease cases, and 41% of certain cancer types [2]. Notably, the prevalence of severe obesity—an important factor in reduced life expectancy—has doubled over the past decade, affecting approximately 2.6 million adults [2].

The current framework for obesity management in the UK consists of a four-tier model. Tier 1 focuses on prevention and is managed by Public Health initiatives. Tier 2 services are community-based, providing referrals to evidence-based lifestyle interventions such as Weight Watchers and the Counterweight Programme. Individuals in Tier 2 typically have a BMI of 28-35 and do not present with complex medical issues. Tier 3 services or specialist weight management services represent a multidisciplinary specialist approach, available in community, primary or secondary care settings. This tier caters to individuals with a BMI greater than 35 (or over 30 if they have diabetes) and complex medical conditions, offering pharmacotherapy, low-energy liquid diets, and pre- and post-bariatric surgery care. Tier 4 services, located within secondary care, focus on bariatric surgery.

Data on obesity rates are systematically collected by the National Audit Office, enabling monitoring of Tier 1 effectiveness. Additionally, the National Bariatric Database provides insights into bariatric surgery rates, patient characteristics, and surgical outcomes [3]. However, comprehensive data on Tier 3 or specialist weight management services remain scarce, with information primarily available from only 4 of the 42 tier 3 clinics. Consequently, it is challenging to ascertain the availability of Tier 3 services across different regions, the volume of referrals, the demographics of individuals accessing these services, and their outcomes during treatment. This lack of data hinders our ability to evaluate equitable access, appropriate referrals, and the overall effectiveness of these services throughout the UK.

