#### SfE CORE Study Protocol

6. **Patient-Reported Outcomes:** Quality of life (EQ5D questionnaire) and well-being (BodyQ questionnaire).
7. **Clinical Treatments:** Interventions received during clinic visits.
8. **Clinical Measures:** Weight, height, BMI, blood pressure.
9. **Relevant Laboratory Results:** HbA1c if has diabetes.

The information gathered through this study will serve to enhance productivity in existing services, inform business planning, and support the establishment of new services. It will also provide critical data to ensure equitable access to weight management services nationwide. Furthermore, the database will function as a registry, enabling researchers to apply for access to data that will advance our understanding and treatment of obesity.

**Study Aim:** This study aims to demonstrate proof of concept for our new data collection system involving a network of weight management clinics across England and Wales. Success would be seen in getting 50% of the current specialist weight management services (there are approximately 49 services at the moment[4]) to capture data on 60% of the patients attending their clinics. Focusing on specialist weight management services in the first instance and then rolling out to other primary care services in a second phase.

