### 3.2 Outcomes

	Objectives	Outcome Measures	Timepoint(s)
Primary	To demonstrate that our system can be integrated into specialist weight management services clinics and collect data on patients attending clinics.	The number of clinics using the system by end of year 2 of the project. Our aim would be to have 50% of specialist weight management services using this system.	24 months
Secondary	To demonstrate that key outcomes are captured in sufficient quantity to give a fair representation of the people attending the clinics	That the clinics on average are collecting data on 60% of the patients that attend their clinics and on these they have at least 80% data on our key outcomes which are  Demographics Age, sex, socioeconomic status, ethnicity, marital status and employment status and Job.	Baseline  Baseline

SfE CORE Study Protocol

		
Weight history Birth weight, age weight problem started at, highest and lowest weight. Current weight.
 
Previous Weight Loss Attempts Previous Bariatric surgery – Y/N – if Y when and Type. Attempts at commercial diets – Y/N if Y when and Type Tried weight loss medication – Y/N if Y when and Type
 
Medical and drug history List of medical problems with date started. List of drugs taking with dose, frequency and start date.
 
Clinical Treatments Diet and Exercise advice Y/N if yes details and date offered Low calorie diet Y/N if yes details and date started and finished. Specific help with eating habits Y/N, If yes details and date (S) delivered Sessions with psychologist Y/N, If yes details and date (s) delivered. Weight loss drugs Y/N if yes which type and when started. Referred for surgery Y/N if yes when.
 
Patient-Reported Outcomes EQ5D and Body Q
 
Clinical Measures Weight, height, BMI, blood pressure.
	
Baseline
 
Baseline and every 12 months until leaves clinic.
 
Baseline and every 12 months until leaves clinic.
 
Baseline and every 12 months until leaves clinic.
 
Baseline and every 12 months until leaves clinic.
 
Baseline and every 12 months until leaves clinic.
 
Baseline and every 12 months until leaves clinic.

--	--	---	---

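### The enrolment projection uses 21 sites, which is 42.9% of the roughly 49 services in the success criterion and four short of the 50% primary target

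*Protocol*

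**What the plan says.** Section 3.2 (Outcomes) gives the primary outcome measure as "The number of clinics using the system by end of year 2 of the project" and adds: "Our aim would be to have 50% of specialist weight management services using this system". The Data analysis part of Section 4 repeats this ("Our aim is to get 50% of specialist weight management service using the database") and undertakes to report both the number of services and the percentage using the app at year 2.

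The Study Aim paragraph at the end of Section 1 ties success to half of the current services and gives their number: "there are approximately 49 services at the moment". Section 3 repeats the criterion for current services and cites the same reference, a web directory, without repeating the count.

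Section 6.2.1 (Size of sample) restates the 50% target. Its next paragraph gives an expected enrolment, "resulting in a total of 41,160 patients across 21 participating sites". It does not explain where 21 comes from.

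A different count appears earlier in Section 1, where data on tier 3 services are called scarce, "with information primarily available from only 4 of the 42 tier 3 clinics". The same section treats tier 3 services and specialist weight management services as one category. The figures 42 and 49 are not reconciled anywhere.

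**The concern.** The site number in Section 6.2.1 follows directly from a restatement of the 50% target, so a reader will take 21 to be that 50%. Against the count attached to the success criterion, it is not.

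The proportion of services using the system is the study's only primary outcome, and the study is a proof of concept judged against it. Section 6.2.1 also links success in gathering adequate data to adoption of the system as the national NHS standard. A team working to 21 sites could believe that it had met the target when, on the stated count, it had not. The projected total of 41,160 patients carries the same mismatch, because it is a direct multiple of the site number.

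**Working it through.** **Inputs**
- Referrals per service per year: 700 (Section 6.2.1)
- Average time in the service: 18 months, i.e. 1.5 years (Section 6.2.1)
- Recruitment period: two years (Section 6.2.1)
- Capture rate used in the projection: 80% (Section 6.2.1)
- Sites in the projection: 21 (Section 6.2.1)
- Services: about 49 (Section 1, Study Aim); 42 tier 3 clinics (Section 1, Background)
- Target: 50% of services (Sections 1, 3, 3.1, 3.2, 4 and 6.2.1)

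**Step 1. Reproduce the plan's total.**
- Existing patients per service: 700 × 1.5 = 1,050
- Potential recruitment per service: 1,050 + 700 + 700 = 2,450
- Enrolled per clinic: 2,450 × 0.80 = 1,960
- Total: 1,960 × 21 = 41,160

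This matches exactly, so the multiplication is sound. The question is only whether 21 is the right multiplier.

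**Step 2. Share of services that 21 sites represent.**
- On 49: 21/49 = 42.9%, which is 7.1 percentage points below target
- On 42: 21/42 = 50.0%

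**Step 3. Sites needed for 50% of 49.**
- 0.50 × 49 = 24.5
- 24/49 = 49.0%, just short; 25/49 = 51.0%, met
- Hence 25 sites are needed, and 25 − 21 = 4 more than projected

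**Step 4. Results for which the two counts disagree.**

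| Sites using the system | Share of 42 | Share of 49 |
|---|---|---|
| 21 | 50.0% | 42.9% |
| 22 | 52.4% | 44.9% |
| 23 | 54.8% | 46.9% |
| 24 | 57.1% | 49.0% |
| 25 | 59.5% | 51.0% |

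From 21 to 24 sites the target is met on 42 and missed on 49. From 25 sites it is met on both.

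**Step 5. Sensitivity to the approximate count.** The protocol says only that there are about 49 services. Assuming nearby values, 47 or 48 services need 24 sites, 49 or 50 need 25, and 51 or 52 need 26. Twenty-one sites reach 50% only if there are 42 services or fewer; at 43 the share is already 21/43 = 48.8%.

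**Step 6. Effect on the projected total, changing the site number only.**
- 25 × 1,960 = 49,000
- Difference: 49,000 − 41,160 = 7,840, i.e. 4 × 1,960, or 19% of the stated total

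**The case against.** **Twenty-one is a projection input, not a site plan.** It appears once, as a multiplier. Section 6.2 aims to recruit from services throughout England and Wales, and the steering committee's duties include suggesting further suitable sites. A reader might infer that the study is designed to fail its own target. The documents do not support that: nothing caps the study at 21 sites, and more can open without a change of design. What stands is that the only site number given does not fit the target restated just before it.

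**Only one count is attached to the criterion.** A reader might infer that the protocol defines two rival denominators, or that it leaves the choice open until the result is known. That is too strong. The figure of 42 occurs only as background on where data already exist. The criterion refers to current services from a cited source, and Section 4 promises the number of services alongside the percentage, so the denominator used would be visible. The link between 21 and 42 is an inference: 42 is simply the only clinic count in the protocol of which 21 is half. The mismatch between 21 and 49 does not depend on it.

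**The count is approximate, and no inference depends on it.** Both are true. There is no formal power calculation, and the target is worded as an aim. But rounding does not explain a gap of seven services. The exact counting date could be in an analysis plan that is not shown; an unseen plan does not remove the conflict between figures in the protocol itself.

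**Conclusion.** The point holds as an internal inconsistency. The success criterion refers to about 49 services and so needs about 25. The projection uses 21, which is 42.9% of 49 and four sites short, and the 41,160 total inherits the error. On the protocol's own 1,960 per clinic, the total consistent with 25 sites is 49,000.

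This rests on taking the protocol's approximate 49 at face value. The integer target moves by about one site for every two services by which that count is wrong, and 21 suffices only at 42 or below.

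A reader might conclude that correcting this makes the target harder to reach. It does not: the target is already half of about 49, and only the projection changes. Nor should the correction be mixed with the separate question of whether the projection should use the 60% patient target instead of 80% capture. The figures here keep the protocol's 80% so that they isolate the site number.

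**What to change.** 1. In Sections 3.2 and 4, state one dated count of specialist weight management services in England and Wales as the denominator of the primary outcome. The Study Aim indicates about 49; the sponsor should confirm it.
2. State the integer target that follows: 25 if the count is 49.
3. In Section 6.2.1, do one of the following:
   - change the site number and total to match (25 sites and 25 × 1,960 = 49,000, at the present capture assumption); or
   - keep 21 and 41,160, and say that 21 sites is an expectation of about 43% of services, below the target.
4. In the Background, say how the 42 clinics relate to the 49 services, or use one count throughout.

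The cost is the sponsor's check of the count and a wording amendment. The design, data collection and 50% target are unaffected. It should be done before the year-2 result is known.
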